2.3 Variables

2.3.1 Primary Variable

The primary variable is the number of target ulcers healed in each group within 16 weeks. The primary efficacy outcome is the comparison of the incidence of complete healing of the target ulcer between the two treatment groups at the end of treatment.

For the purpose of this study a complete healing will be defined as complete epithelialization which is maintained with no drainage for at least 2 weeks and is confirmed by a blinded independent evaluator.

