2.3.2 Secondary Variables

The secondary efficacy outcomes are:

- ✓ Time to complete ulcer healing,
 The time of the original healing will be taken as the time to healing.
- ✓ Percentage change in ulcer surface area from baseline,
- ✓ Percentage of subjects with a 50% reduction of ulcer surface area,
- ✓ Incidence of infection of the target ulcer.

Safety outcomes include assessment of the incidence of treatment-emergent adverse events, clinical laboratory values, and vital signs.

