3.2 Inclusion Criteria

Subject is eligible for the study if all of the following apply:

1. Has signed a written informed consent prior to the first study evaluation
2. Male or female is at least 20 and < 80 years of age
3. Diabetes mellitus (type 1 or 2) with an HbA1c < 12.0% measured during screening or within three months prior to randomization
4. An ankle brachial index on the target limb at least 0.8 measured during screening or within three months prior to randomization
5. The target ulcer must have the following characteristics:
 - a、 Grade 1 or 2 per Wagner Ulcer Classification System
 - b、 No higher than the ankle
 - c、 No active infection
 - d、 A cross-sectional area of between 1 and 25 cm² post-debridement
 - e、 Present for at least 4 weeks before randomization
6. If female and of childbearing potential has a negative pregnancy test and is not breastfeeding at screening visit
7. Able and willing to attend the scheduled visits and comply with study procedures

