3.4 Discontinuation Criteria for Individual Subjects

A discontinuation is a subject who is randomized into the study and for whom study treatment is terminated prematurely for any reason.

The subject is free to withdraw from the study intervention and/or study for any reason and at any time without giving reason for doing so and without penalty or prejudice. The investigator is also free to terminate a subject's involvement in the study at any time if the subject's clinical condition warrants it.

Discontinuation Criteria for Individual Subjects:

1. Violation and/or significant deviation of study protocol
2. Lack of efficacy satisfactory (defined as a worsening of Wagner grade to level of 3)
3. Safety concerns
4. Lost to follow-up
5. Withdrawal consent;
6. In the Investigator's opinion, it is in the patient's best interest;
7. Termination of study by the sponsor.

In all cases, the reason for and date of withdrawal must be recorded in the case report form (CRF) and in the subject's medical records. The subject must be followed up to establish whether the

reason was an adverse event, and, if so, this must be reported in accordance with the adverse events reporting procedures.

If a subject withdraws from the study or the study intervention is discontinued prematurely, all procedures as scheduled at the end of the trial should be included on the case report form.

There will be no replacement of withdrawn subjects, regardless of the reason for withdrawal. All subjects who experience adverse event which is ongoing either at the time of withdrawal or at the post study visit, must be followed-up at appropriate time intervals until the adverse event is resolved or judged to be no longer clinically significant, or until they become chronic to the extent that they can be fully characterized.

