5.1.3 Comparative Period

(Visit 3-Visit 10: Day 15 to Day 113)

The following procedures will be performed in this period:

- Apply test medication or comparative intervention

If complete wound healing by the judgment of independent reviewer happens before Visit 10, the applied test medication (ON101 cream) or comparative intervention (Aquacel® Hydrofiber® dressing) will be stopped at next scheduled visit which will be deemed as V10.

If the wound is unhealed at Visit 10, only Aquacel® Hydrofiber® dressing will be applied.

- Perform physical examinations and obtain vital signs
- Perform laboratory tests including hematology and biochemistry at Visit 4, Visit 6, Visit 8, Visit 10 and at the visit of early permanent discontinuation of study treatment
- 12 Lead ECG examination will be performed at Visit 10 or at the visit of prematurely discontinuation of study treatment
- Perform assessment of foot ulcer status and photography
- Standard ulcer care
- Perform assessment of adverse events
- Record concomitant medication

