5.2.2.2 Concomitant Medication (Drugs and Therapies)

If the administration of any concomitant treatment becomes necessary, it must be reported in the case report form and in the subject's medical records. As far as possible, minimum changes (dose, frequency) should be made to the concomitant treatment during the study. However, concomitant medications should be kept to a minimum during the study. The sponsor must be consulted if there is any doubt, and a decision to withdraw the subject must be made jointly by the sponsor and the investigator.

Permitted concomitant medication

Oral and/or intravenous antimicrobial agents are allowed for treatment of presumed infection.

Prohibited concomitant medication

Topical antimicrobials and agents known to affect wound healing are not allowed during the study treatment period.

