5.5.2 Adverse Events

Adverse event collection will begin after study intervention initiated and continue through the entire study visit. All observed or spontaneously reported AEs will be recorded in the source documents and CRFs. Data to be recorded includes a description of the event, date of onset and end of the event, severity, action with respect to study intervention, treatment required, relationship to study intervention, and outcome of the event.

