7.4.2 Analysis of Secondary Variables

The secondary efficacy variables will be analyzed using FAS population.

- Time to complete ulcer healing:

Time to complete ulcer healing will be calculated for all subjects from the day of the first study medication applied until the day that original healing of target ulcer is first observed. Subjects who could not achieve complete ulcer healing at the last evaluation time point will be censored (non-healing) at the date of last evaluation. The median time to complete ulcer healing will be estimated by Kaplan-Meier method and two-sided 95% confidence interval will be reported. The log-rank test will be performed for comparing time to complete ulcer healing among two groups.

- Percentage change in ulcer surface area from baseline:

Summary statistics of the measured wound size and the percentage change from baseline will be obtained for each group by observation time point and their changes over time will also be graphically presented.

For the analysis on the ulcer surface area, the percentage change from baseline at each visit will be calculated using the actual wound size. The wound size percentage change will be compared between groups by means of analysis of co-variance (ANCOVA) adjusted with baseline measurement of sizes and baseline Wagner grade.

- Percentage of subjects with a 50% reduction of ulcer surface area:

The proportion of subjects who achieve 50% reduction of wound size from baseline to interim visit will be calculated for two groups and analyzed by a logistic regression model with treatment as factor, and baseline wound size and Wagner grade as covariates.

- Incidence of infection of the target ulcer:

The incidence of infection of the target ulcer will be summarized and tabulated by two treatment groups at the final ulcer assessment. The incidence of infection of target ulcer between two groups will be compared using Fisher's exact test.

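### Target-ulcer infection is tabulated at one undefined final assessment, so infections that resolved earlier can drop out of this secondary comparison

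*Combined protocol and SAP*

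**What the plan says.** Section 2.3.2 lists "Incidence of infection of the target ulcer" as a secondary efficacy outcome, with no time window and no counting rule. Section 7.4.2 places the secondary variables in the full analysis set (FAS) and adds: "The incidence of infection of the target ulcer will be summarized and tabulated by two treatment groups at the final ulcer assessment". The next sentence names Fisher's exact test for the same quantity and gives no other window.

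Other provisions bear on how the rule would work:

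- Section 3.2 requires of the target ulcer "No active infection" at entry.
- Section 5.2.2.2 states: "Oral and/or intravenous antimicrobial agents are allowed for treatment of presumed infection".
- Section 5.1.3 says that when a wound heals before Visit 10, treatment "will be stopped at next scheduled visit which will be deemed as V10".
- Section 2.3.1 defines healing as "complete epithelialization which is maintained with no drainage for at least 2 weeks", confirmed by the blinded evaluator.
- The schedule of assessments has ulcer assessments at every visit through Visit 14 (Week 28).
- Section 7.2 leaves analysis detail to a separate SAP.

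**The concern.** Incidence ordinarily means new occurrences over a period, but the rule ties the count to one time point. Entry excludes active infection, so every target-ulcer infection on study is new. Systemic antimicrobials are allowed, so an infection can clear before the final assessment. Taken literally, the table then shows subjects infected at that assessment, not subjects who had an infection.

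Two things are at stake. The first is lost events and lost power in a comparison that is informative for a wound product. The second is reproducibility: the sentence lets two analysts produce different tables, because neither the counting rule nor the visit is fixed.

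**Working it through.** **Text check.** In the supplied text, no infection rule refers to a cumulative count, to any time on study, or to at least one episode. Where the plan means a period it says so: Section 7.4.3 counts recurrence over the three-month follow-up, and Section 7.4.2 runs time to healing from first application to first observed healing. The missing-data rule in Section 7.7 does not repair this, because last observation carried forward carries the latest status and not an ever-infected status.

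**Inputs.** 118 subjects per arm and assumed healing of 50% versus 30% come from Section 7.1. The test comes from Section 7.4.2. Infection rates, durations and the two-sided 0.05 level for this variable are not given and are assumptions here. The plan has no figure for infection to reproduce.

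**Step 1: loss of power when episodes resolve.** Let s be the share of infections still present at the final assessment, equal in both arms. Then p(final) = s × p(ever). With an assumed 25% versus 10% ever infected, exact power by full enumeration of Fisher's test is:

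| s | p(final) | Expected counts of 118 | Power |
|---|---|---|---|
| 1 | 25% vs 10% | 29.5 vs 11.8 | 83.2% |
| 0.75 | 18.75% vs 7.5% | 22.1 vs 8.9 | 67.1% |
| 0.5 | 12.5% vs 5% | 14.8 vs 5.9 | 43.9% |
| 0.25 | 6.25% vs 2.5% | 7.4 vs 3.0 | 17.6% |

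The risk ratio stays at 2.5, but the difference shrinks from 15 to 3.75 percentage points. As a single-table example, 30 versus 12 subjects gives p = 0.003; with half the episodes resolved, 15 versus 6 gives p = 0.065.

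**Step 2: does the single-visit count also pick up healing?** If the final assessment is Visit 10, it falls on a closed wound in 118 × 0.50 = 59 versus 118 × 0.30 = 35.4 subjects. Suppose infection clears when the ulcer heals, infected subjects heal at k times the arm's rate h, and a share u of infections in unhealed ulcers is still present. Then p(final) = p(ever) × (1 − k × h) × u. With the same p(ever) in both arms, so no true difference:

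| p(ever) | k | u | p(final), ON101 vs control | Rejection rate |
|---|---|---|---|---|
| 20% | 1 | 1 | 10% vs 14% | 11.1% |
| 20% | 0.5 | 1 | 15% vs 17% | 4.8% |
| 20% | 1 | 0.5 | 5% vs 7% | 5.2% |
| 10% | 1 | 1 | 5% vs 7% | 5.2% |
| 10% | 0.5 | 1 | 7.5% vs 8.5% | 3.2% |

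The cumulative count rejects 3.5% of the time at 20% ever infected and 2.8% at 10%. Only the first row is clearly above the nominal 5%.

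**The case against.** The strongest reply is that this is loose wording. The variable is named as an incidence, the phrase about the final assessment can be read as the cut-off of a cumulative table, and the sentence naming the test carries no time point. The separate SAP may already hold a cumulative rule. That stands as a possibility, but the supplied text does not contain such a rule.

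The second reply is that the episodes are not lost to the trial. Section 5.5.2 says "Data to be recorded includes a description of the event, date of onset and end of the event, severity", and Section 7.5 tabulates treatment-emergent events and allows a Fisher comparison of their incidence where appropriate. On early exit, Section 3.4 says "all procedures as scheduled at the end of the trial should be included on the case report form", so an infection present then should be seen. This also stands and limits the harm. It does not replace the secondary analysis, because those tables are organised by preferred term, use the safety set, and are not specific to the target ulcer.

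A reader might infer more than the documents support:

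- **That the final assessment must be Visit 10.** Ulcers are assessed through Week 28, and the text does not choose.
- **That no infection in a healed subject could be counted.** The healing definition does not mention infection, and Section 5.3.3 allows cellulitis at Wagner Grade 0, where there is no open lesion. An infection drops out only if it has itself resolved.
- **That the comparison is biased toward ON101 with an inflated false-positive rate.** The 11% figure needs 20% infected, no resolution on antimicrobials and healing independent of infection. The other settings tried give about 3% to 5%.

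**Conclusion.** The concern holds in a limited form. The counting window is undefined, and the literal reading gives status at one visit, which drops infections that resolved earlier. The demonstrable harm is lost events and lost power. How much is unknown, because it depends on infection rates and durations that the documents do not give; the fall from 83% to 18% rests on the assumed 25% versus 10% and on equal resolution in both arms. If resolution goes with healing, the count may also partly reflect healing, but no material type I error inflation is shown. Fewer new infections because wounds close sooner is part of the treatment effect and is not criticised. The variable is secondary, and the primary analysis and interim boundaries are untouched. Severity is minor.

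**What to change.** In Section 7.4.2, replace the reference to the final ulcer assessment with the number and proportion of FAS subjects who have at least one target-ulcer infection, recorded at an ulcer assessment or as an adverse event attributed to the target ulcer, from first treatment through a stated visit. That visit could be Visit 10 or the early-exit visit, with follow-up infections summarised separately. Keep Fisher's exact test, and keep single-visit status as a descriptive table with its visit named. Because entry excludes active infection, no baseline adjustment is needed. If the separate SAP already has a cumulative rule, align this sentence with it.

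The cost is a wording amendment to a secondary variable after the first interim analysis, so it should be made and dated before the second. For completed visits it relies on existing adverse-event and source records; Sections 5.3.3 and 5.4 name no dedicated infection item. Infection is judged by investigators who know the allocation (Section 4.4), which the new wording does not change. Some dependence on healing will remain, since closed wounds are at less risk of new infection.

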7.4.3 Analysis of Exploratory Variables

The exploratory variable will be analyzed for those subjects whose target ulcer complete healed at the end of comparative period, the recurrences of target ulcer within 3-month follow-up period will be compared between two groups by Fisher's exact test.

7.5 Analysis of Safety

Adverse events will be regarded as Treatment Emergent (TEAE) if they started on or after the date and time of administration of the first dose of study intervention or if they were present prior to the administration of the first dose of study intervention and increased in severity during the study.

Adverse Events (AEs) will be coded using the standard Medical Dictionary for Regulatory Activities (MedDRA) dictionary and grouped by system organ class and preferred term and events. TEAEs will be summarized by frequency and proportion of total subjects, by system organ class and preferred terms. If appropriate, the incidence of adverse events (preferred terms and system organ class) will be compared for each of the two treatment groups using Fisher's exact test.

For the clinical laboratory and vital signs data, the data will be tabulated by treatment group for raw data and for change from baseline to evaluated time points; descriptive statistics to be provided include: n, mean, median, standard deviation, minimum and maximum. The differences between groups will be analyzed by analysis of covariance (ANCOVA) with factor being fitted for treatment, and baseline value fitted as a covariate. Subjects with laboratory data outside the normal range will be listed and abnormal values will be flagged.

7.6 Interim Analysis (and Early Discontinuation of the Clinical Study)

7.6.1 Early Discontinuation

The Independent Data Monitoring Committee (IDMC) will review the results of the interim analysis for a possible early termination of the trial. The statutes of the IDMC will be defined in advance and will be included in a separate charter. To avoid possible bias, unless a decision is made to terminate the trial, the IDMC will not disclose any results other than the recommendation to continue the trial.

7.6.2 Interim Analysis

Two Interim Analyses will be conducted when 118, and 212 subjects complete the comparison period or early withdraw from study intervention on a sequential basis. This will be about 50% and 90% of the total number of subjects that will be randomized.

The independent Data Monitoring Committee (IDMC) will review the results of the interim analyses for a possible early termination of the trial due to an overwhelming efficacy results based on pre-defined alpha specified based on O'Brien-Fleming alpha-spending function specified in this protocol and detailed in the Statistical Analysis Plan(SAP). The statutes of the IDMC will be defined in advance and will be included in a separate charter.

The Lan and DeMets version (Lan and DeMets, 1983) of the O'Brien-Fleming alpha-spending function is used to calculate the Type I Error rate alpha, to maintain the trial-wise 5% type I error. Because the 1st interim analysis has been conducted at 124 subjects who complete the comparison period, the alpha boundary will be estimated based on 53% information for the 1st interim analysis. The proportion of the overall number of target subjects (a total of 236 subjects) included in the analyses at each point and alpha boundaries used to assess significance at each analysis are as follows.

Analysis number	% of randomized subjects	Alpha Boundary
1. Interim Analysis 1	53%	0.003957
2. Interim Analysis 2	90%	0.034760
3. Final	100%	0.039611

As the 1st IA failed to meet the boundary of (0.003957); a 2nd IA will be conducted. Based on the above mentioned boundary for the 2nd IA, the IDMC can stop the trial if the observed p-value is less than 0.034760, the alpha presented above.

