7.4 Analysis of Efficacy

7.4.1 Analysis of Primary Variable

The primary efficacy variable is the proportion of subjects whose target ulcer is complete healing. The definition of complete healing for the target ulcer is complete epithelialization which is maintained with no drainage for at least 2 weeks and is confirmed by a blinded independent evaluator.

This will be a multi-center study. It is anticipated that the number of participating centers can be large and the number of subjects enrolled at each center could be small. As a result, the data from all centers will be pooled for statistical analyses.

The hypothesis for the comparison is given as follows:

H_0 : The healing rates on ON101 cream and Aquacel® Hydrofiber® dressing are the same

H_1 : The healing rates on ON101 cream and Aquacel® Hydrofiber® dressing are not the same

The number of percentage of subjects achieving the efficacy endpoints will be summarized by visit and ON101 cream group will be compared to the Aquacel[®] Hydrofiber[®] dressing group with Chi-square test. The logistic regression model with treatment/intervention as fixed factor, and baseline wound size and Wagner grade as covariates will be applied to the primary analysis of primary endpoint. The results of the logistic regression model will be presented in terms of the odd ratio (ON101 cream versus Aquacel[®] Hydrofiber[®] dressing), with p-values and associated 95% confidence intervals of the odds ratio.

The test intervention (ON101 cream) will be concluded to be superior to the control (Aquacel[®] Hydrofiber[®] dressing) in average if the null hypothesis (H_0) is rejected and the odds ratio higher than 1. To reflect the interim analysis, final analyses will be based on a Type I error rate (two-sided) of 0.039611.

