10.1 Independent Data-Monitoring Committee (IDMC)

An Independent Data Monitoring Committee (IDMC) will be formed to evaluate the outcome and safety and tolerability issues that may arise during the conduct of the study according to the IDMC Charter. The IDMC will consist of 3 members. Two members will constitute a quorum. The IDMC includes experts in or representatives of the fields of clinical medicine, in particular expertise related to the disease being studied, clinical trial methodology, including safety review, assessment, and reporting biostatistics. It is essential that the judgment of members of the IDMC not be influenced by factors other than those necessary to maintain subject safety and to preserve the integrity of the trial. Independence is essential to ensure that IDMC members are objective and capable of an unbiased assessment of the trial's safety and efficacy data.

The IDMC will review two formal interim efficacy and safety analyses at the time when the 118 and 212 subjects (50% and 90% of the total number of randomized subjects) have completed the comparison period or early withdrawn from study intervention. During the randomized portion of the study, the trial may be stopped early if the ON101 cream arm appears to be insufficiently efficacious, significantly more efficacious, or if there are unacceptable toxicities.

The critical nature of interim decision means that the investigators and the sponsor must provide complete, timely and accurate interim data. Following the interim review, the IDMC will forward to the sponsor its recommendation regarding whether to continue the study as planned.

Apart from these formal interim analyses, the IDMC may periodically monitor the overall safety results. To avoid possible bias, unless a decision is made to terminate the trial, the IDMC will not disclose any results other than the recommendation to continue the trial.

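### The second interim efficacy set is undefined; read as the completers to date, it over-represents early healers and slightly favours whichever arm heals faster

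*Combined protocol and SAP*

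**What the plan says.** Section 7.6.2 times the looks by the number of subjects who "complete the comparison period or early withdraw from study intervention on a sequential basis". Section 10.1 uses the same count, of subjects who "have completed the comparison period or early withdrawn from study intervention". Section 7.6.2 introduces its table of boundaries as "The proportion of the overall number of target subjects (a total of 236 subjects) included in the analyses at each point", with 53%, 90% and 100%, and reports the first look this way: "Because the 1st interim analysis has been conducted at 124 subjects who complete the comparison period". At the second look, "the IDMC can stop the trial if the observed p-value is less than 0.034760". Section 7.4.1 adds that "final analyses will be based on a Type I error rate (two-sided) of 0.039611".

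The comparison period does not have the same length for everyone. Section 5.1.3 provides: "If complete wound healing by the judgment of independent reviewer happens before Visit 10", study treatment "will be stopped at next scheduled visit which will be deemed as V10". The footnote to the schedule of assessments also makes premature discontinuation of treatment a Visit 10.

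The full analysis set (section 7.2.1) is all randomized subjects, with no interim version. Section 7.7 offers LOCF, and gives no rule for subjects still inside their 16 weeks at an interim data cut.

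**The concern.** If the 212 analysed subjects are those who have finished by the cut, entry to the set depends on the outcome. A healer confirmed at Week 6 is in; an unhealed subject randomized on the same day is not in until Week 16, unless withdrawn.

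The primary hypothesis in section 7.4.1 is equality of healing rates. Time to healing is a separate, secondary endpoint. If ON101 only brought healing forward, without healing more ulcers by Week 16, an outcome-dependent set could present speed as a difference in rate. The second look can end the trial for efficacy, so that is where a false claim would arise. Superiority is claimed only for an odds ratio above 1, so the relevant error is the tail favouring ON101. The two-sided total partly hides it, because the opposite tail shrinks.

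**Working it through.** **1. The plan's own figures.** 124/236 = 0.525 and 212/236 = 0.898. Lan-DeMets O'Brien-Fleming spending with 0.025 in each tail, at information 0.525, 0.898 and 1, gives two-sided levels of 0.003957, 0.034757 and 0.039611. The plan states 0.003957, 0.034760 and 0.039611, so the boundaries reproduce. The nominal chance of crossing in one direction at the second look alone is 0.034760/2 = 1.7%.

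**2. Effect on each arm's rate.** 236 - 212 = 24 subjects are outside the set. With 40% healing there are 0.40 × 236 = 94.4 healers. If none of the 24 ever healed, the interim rate would be 94.4/212 = 44.5%, an upper limit of +4.5 points. In the simulations 19% to 33% of the 24 later heal:
- 19%: (94.4 - 4.6)/212 = 42.4%
- 33%: (94.4 - 7.9)/212 = 40.8%

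The pooled rate is then overstated by roughly 0.8 to 2.4 points.

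**3. Effect on the odds ratio.** In arm j let p_j be the true healing rate, a_j the share of eventual healers already in the set, and b_j the same share for eventual non-healers. The odds seen at the interim are p_j·a_j / [(1 - p_j)·b_j], so

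OR(interim) = OR(true) × (a_1/a_0) × (b_0/b_1).

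If timing is the same in both arms, a_1 = a_0 and b_1 = b_0, and the odds ratio is unchanged even when one arm heals more. If one arm's healers close earlier, its a_j is larger and the odds ratio moves toward that arm. Withdrawals, mostly non-healers, also enter early; this raises b_j and reduces the over-representation of healers.

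**4. Size at the second look.** Simulated trials of 236 subjects: 1:1 blocks, uniform accrual, healing confirmed 2 weeks after first closure, and a pooled z-test at 0.034760 in place of the adjusted logistic model. Accrual, healing times and withdrawal are assumptions. The first two rows use 10% withdrawal among non-healers; the last three use none.

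| Assumed truth | First 212 to complete | First 212 randomized |
|---|---|---|
| 40%/40%, 5 vs 10 weeks, accrual 60-156 weeks | difference +0.8 to +1.8 points; false superiority 2.2-3.0% | no bias; 1.6-1.9% |
| 40%/40%, 7 vs 10 weeks, same accrual | +0.5 to +1.1 points; 2.1-2.5% | no bias; 1.7-1.8% |
| 50%/30%, same timing, accrual 104 weeks | OR 2.32 | OR 2.32 |
| 50%/30%, ON101 faster, 104 weeks | OR 2.41; crossing 0.85 | OR 2.33; 0.80 |
| 50%/30%, ON101 slower, 104 weeks | OR 2.24; crossing 0.78 | OR 2.33; 0.81 |

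With equal rates and equal timing there is no bias.

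**5. Size over all three looks.** True rates 40%/40%, a strong timing contrast, 10% of subjects withdrawing (all of them non-healers), completion order at both interims, 20,000 runs:

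| Accrual | Tail favouring faster arm | Other tail | Two-sided total |
|---|---|---|---|
| 52 weeks | 3.3% | 2.1% | 5.4% |
| 104 weeks | 2.9% | 2.2% | 5.1% |
| 208 weeks | 2.7% | 2.4% | 5.1% |

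With randomization order the favourable tail was 2.7%, 2.4% and 2.6%. The simulation error of a tail is √(0.025 × 0.975/20,000) = 0.11 points, so the 208-week result is hardly distinguishable from 2.5%.

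**The case against.** **The text may give only the timing.** Section 7.6.2 says when the looks take place, and its reference to a sequential basis can describe the looks. Section 7.2.1 makes all randomized subjects the efficacy population, and the separate SAP and IDMC charter may define the set; neither is in the text reviewed. This stands in part: completion order is the likely reading, supported by the table's reference to subjects included, but it is not stated. The alternative does not help. Analysing everyone randomized by that date, with unhealed subjects carried forward under section 7.7, gave a false difference of +0.8 to +2.6 points and a false crossing of 2.4% to 4.8% under the step 4 assumptions for equal rates.

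**The bias is conditional and small.** This stands. It needs different healing times among healers, the documents give no healing time for the dressing, and the bias runs against ON101 if ON101 healers are slower. The two-sided 5% level, the protocol's stated criterion, is hardly disturbed.

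**Changing the set between looks has a price.** This also stands. The first look has already been run on 124 completers, leaving 236 - 124 = 112 subjects outside the set, and the same mechanism applied there. Ordering by randomization also sets aside some later entrants' completed results, although section 7.7 says that all available data will be used.

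**Conclusion.** The plan should define the second interim set. On the natural reading healers are over-represented, and if healing times differ between arms the comparison favours the faster arm. Under the assumptions in step 4 the false difference is about +0.5 to +1.8 points, and the chance of a false superiority crossing is about 2.1% to 3.0% against a nominal 1.7%. Over all looks, with a strong timing contrast, the favourable tail is about 2.7% to 3.3% against 2.5%, and the two-sided total is 5.1% to 5.4%. The final analysis of 236 subjects is unaffected. The effect is modest, but the correction is cheap and this look can stop the trial.

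A reader might infer three stronger points that the documents do not support:
- That all the subjects left out are non-healers. Some are healed and awaiting confirmation, some are recent entrants who will heal, and with slow accrual some are not yet randomized.
- That the plan prescribes a set filled in order of completion. It leaves the set undefined.
- That the interim is biased toward ON101 as such. A higher healing rate with the same timing leaves the odds ratio essentially unbiased.

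**What to change.** In sections 7.6.2 and 10.1, the SAP and the IDMC charter:
- Define the second interim efficacy set as the first 212 subjects in order of randomization, analysed once each has reached Day 113 or has ended the comparison period early through confirmed healing or withdrawal. Compare the p-value from this set with 0.034760. The share is still 212/236, so the boundary does not change.
- State that subjects randomized later, including any still inside their 16 weeks, are left out of the interim p-value and are not carried forward by LOCF.
- Record that the definition was set after the first look at 124 completers, and without reference to its unblinded results.

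In the simulations this removes the bias whatever the healing times. It costs a short text change in each document and about 2 to 3 weeks' delay to the look. Results from some later entrants who have already completed wait for the final analysis. No extra subjects or visits are needed.
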